14.5 ATTACHMENT 5: Patient Diary of Daily Heart Rate and Blood Pressure Readings

Week 0 through Week 2: (#) ____ capsules per day (#, as directed by physician)

Each morning, please monitor your blood pressure and heart rate. You should be sitting down and at rest **for at least five minutes** before taking your blood pressure and heart rate. The numbers you write down should be the same as those that appear on the monitor screen (do not round the numbers up or down). In the comments section, please write down anything that could have affected your reading, such as feeling unwell or changes in your medication.

NOTE: If your heart rate above 110 or your Systolic Blood Pressure is below 100, please call your doctor.

Date	Time	Heart Rate	Systolic BP (top number)	Diastolic BP (bottom number)	Study Drug # of capsules taken daily	PLEASE CHECK IF YOU ARE EXPERIENCING ANY OF THE FOLLOWING:
						 Palpitations  Light headedness  Chest pain  Worsening shortness of breath  Worsening edema (swelling)  Other _____
						 Palpitations  Light headedness  Chest pain  Worsening shortness of breath  Worsening edema (swelling)  Other _____

Week 2 through Week 4: (#) _____ capsules per day (#, as directed by physician)

Each morning, please monitor your blood pressure and heart rate. You should be sitting down and at rest **for at least five minutes** before taking your blood pressure and heart rate. The numbers you write down should be the same as those that appear on the monitor screen (do not round the numbers up or down). In the comments section, please write down anything that could have affected your reading, such as feeling unwell or changes in your medication.

NOTE: If your heart rate above 110 or your Systolic Blood Pressure is below 100, please call your doctor.

Date	Time	Heart Rate	Systolic BP (top number)	Diastolic BP (bottom number)	Study Drug # of capsules taken daily	PLEASE CHECK IF YOU ARE EXPERIENCING ANY OF THE FOLLOWING:
						 Palpitations  Light headedness  Chest pain  Worsening shortness of breath  Worsening edema (swelling)  Other _____
						 Palpitations  Light headedness  Chest pain  Worsening shortness of breath  Worsening edema (swelling)  Other _____

Week 4 through Week 6: (#) _____ capsules per day (#, as directed by physician)

Each morning, please monitor your blood pressure and heart rate. You should be sitting down and at rest **for at least five minutes** before taking your blood pressure and heart rate. The numbers you write down should be the same as those that appear on the monitor screen (do not round the numbers up or down). In the comments section, please write down anything that could have affected your reading, such as feeling unwell or changes in your medication.

NOTE: If your heart rate above 110 or your Systolic Blood Pressure is below 100, please call your doctor.

Date	Time	Heart Rate	Systolic BP (top number)	Diastolic BP (bottom number)	Study Drug # of capsules taken daily	PLEASE CHECK IF YOU ARE EXPERIENCING ANY OF THE FOLLOWING:
						 Palpitations  Light headedness  Chest pain  Worsening shortness of breath  Worsening edema (swelling)  Other _____
						 Palpitations  Light headedness  Chest pain  Worsening shortness of breath  Worsening edema (swelling)  Other _____

Week 6 through Week 8: (#) _____ capsules per day (#, as directed by physician)

Each morning, please monitor your blood pressure and heart rate. You should be sitting down and at rest **for at least five minutes** before taking your blood pressure and heart rate. The numbers you write down should be the same as those that appear on the monitor screen (do not round the numbers up or down). In the comments section, please write down anything that could have affected your reading, such as feeling unwell or changes in your medication.

NOTE: If your heart rate above 110 or your Systolic Blood Pressure is below 100, please call your doctor.

Date	Time	Heart Rate	Systolic BP (top number)	Diastolic BP (bottom number)	Study Drug # of capsules taken daily	PLEASE CHECK IF YOU ARE EXPERIENCING ANY OF THE FOLLOWING:
						 Palpitations  Light headedness  Chest pain  Worsening shortness of breath  Worsening edema (swelling)  Other _____
						 Palpitations  Light headedness  Chest pain  Worsening shortness of breath  Worsening edema (swelling)  Other _____

NYHA	New York Heart Association
PH-HFpEF	Pulmonary Hypertension with Heart Failure and Preserved Left Ventricular Ejection Fraction
PK	Pharmacokinetic
PP	Per-Protocol
PR	Pulse rate
QID	Four times daily
QOL	Quality of life
SAE	Serious adverse event
SAP	Statistical Analysis Plan
SAS®	Statistical Analysis Software®
TEAE	Treatment-emergent adverse event
TFL	Tables, Figures and Listings
TID	Three times daily
WHO	World Health Organization

1 INTRODUCTION

The purpose of this Statistical Analysis Plan (SAP) is to provide a description of the statistical methods to be implemented for the analysis of data from the study with protocol number TNX-LVO-05. The SAP will be finalized prior to database lock. Any deviations from the SAP after database lock will be documented in the final Clinical Study Report (CSR).

2 STUDY OVERVIEW

2.1 Study Objectives

The study objective is to continue treatment of levosimendan in patients who were participating in a Tenax-sponsored study after completion of the parent study. This open-label rollover study is designed to allow patients to continue levosimendan treatment if the patient has tolerated treatment in a clinical study sponsored by Tenax Therapeutics Inc. (the parent study) and if, in the opinion of the Investigator, the patient may benefit from continued levosimendan treatment. Patient safety will be evaluated in accordance with institutional standards of care.

2.1.1 Primary Objectives

The primary objectives are to evaluate the safety and tolerability of levosimendan in extended use after completion of the parent study.

2.1.2 Secondary Objective

The secondary efficacy objective is to evaluate whether the effectiveness of daily oral levosimendan is sustained in extended use.

2.1.3 Exploratory Objectives

No exploratory objectives are itemized for the study.

2.1.4 Pharmacokinetic (PK) Objectives

There are no PK objectives for this study.

2.2 Study Design

2.2.1 Overview

This extension study is designed to investigate the safety and efficacy of extended levosimendan in patients who previously received levosimendan in the Pulmonary Hypertension with Heart Failure and Preserved Left Ventricular Ejection Fraction (PH-HFpEF) study sponsored by Tenax and may, in the investigator's opinion, derive benefit from continued treatment. Patients will be screened for eligibility at the last visit in the treatment period of the parent study. Eligible patients will be enrolled into the study immediately upon confirmation of eligibility so that levosimendan is not interrupted.

Efficacy assessments (Six-minute walk test (6MWT), Patient global assessment (based on the Kansas City Cardiomyopathy Questionnaire (KCCQ) instrument), Physician's Assessment of Functional Class (measured by New York Heart Association (NYHA) functional class assessment), Clinical Events (death and hospitalizations)) will be performed at 3, 6, 12, 24, 48 weeks and yearly through the Follow-up/Termination visit. Patients will undergo a follow-up visit (at termination) as soon as possible after study drug discontinuation, but within one (1) week.

Patients whose blood pressure (BP) falls below the specified range will be queried regarding any symptoms of hypotension which may result in the down titration of the levosimendan dose. Patients whose heart rate exceeds the specified range will be queried regarding symptoms of worsening heart failure. An excessive heart rate in a patient with no evidence of worsening heart failure, suggests that the increased heart rate is a direct drug effect requiring a down titration of the levosimendan dose.

2.2.2 Randomization and Blinding

This is an open-label extension of the parent study. All patients who enroll into this study will receive an open-label levosimendan. No blinded treatment assignments are required.

2.2.3 Study Drug and Dosing Regimen

All patients entering the study will continue receiving intravenous (IV) levosimendan weekly, and some of them will be transitioned to an oral dose of levosimendan. Those currently receiving IV levosimendan weekly will return to the investigational site and receive 1mg levosimendan capsule daily for two weeks.

Patients may then be titrated up every 2 weeks at 1mg levosimendan increments up to maximum of 4 mg daily (1mg QID), based on assessments of safety and patient's clinical response. Patients who tolerate 3 mg (1mg TID) oral levosimendan TID that have not demonstrated a 6MWT equivalent or better than the recorded 6MWT at initiation of their IV to oral levosimendan may be titrated to 4 mg (1mg QID). Patients who experience identified safety concerns in should be down-titrated at 1 mg/day increments or discontinued at the physician's discretion.

2.2.4 Sample Size Determination

All patients completing the parent study and in the opinion of the Investigator, may benefit from continued treatment.

2.3 Study Endpoints

2.3.1 Primary Endpoints

The primary endpoints are the incidence and severity of adverse events (AEs) and the incidence and severity of abnormal clinical laboratory test results (hematology, chemistry), physical examinations, vital signs ([BP] and pulse rate [PR]) and 12-lead electrocardiogram (ECG) values.

2.3.2 Secondary Endpoints

The secondary efficacy endpoints of the study are measures assessed at Weeks 3, 6, 12, 24 and 48, and yearly through the follow-up/termination visit:

- 6-minute walk test (6MWT),
- Patient global assessment (based on the Kansas City Cardiomyopathy Questionnaire (KCCQ) instrument),
- Physician's Assessment of Functional Class (measured by the NYHA functional class assessment), and
- Clinical Events: Death and hospitalizations.

2.3.3 Exploratory Efficacy Endpoints

There are no exploratory efficacy endpoints.

2.3.4 Pharmacokinetic (PK) Endpoints

There are no PK endpoints for this study.

3 STATISTICAL METHODOLOGY

3.1 General Considerations

3.1.1 Analysis Day

Analysis day will be calculated from the date of first dose of study drug (first IV dose or first oral dose, whichever occurs first). The day of the first dose of study drug will be Day 1, and the day immediately before Day 1 will be Day -1. There will be no Day 0.

3.1.2 Analysis Visits

Scheduled visits will be assigned to analysis visits as recorded on the case report form (CRF).

3.1.3 Definition of Baseline

Baseline is defined as the last non-missing measurement prior to the first dose of study drug.

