8.1.3.1 Quality of Life Assessments

The 6-point Likert scale will be replaced with the KCCQ instrument ([Attachment 2](#)) and provided to subjects to completed as per the [Time and Events Schedule](#).

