3.2 Analysis Populations

3.2.1 Safety Analysis Set (SAF)

The Safety Analysis Set (SAF) will consist of all patients who receive at least 1 dose of study drug. Patients will be analyzed according to dose received, summarized by IV dosing period, oral dosing period, and in total. The SAF will be used for the analysis of safety data.

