3.4.3 Subgroup Analyses

No subgroup analyses will be performed for this study.

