3.5.1 Adverse Events (AEs)

Adverse events will be coded according to the MedDRA guidance version 21.0. An adverse event is considered treatment-emergent if the start date/time of the event is:

- On or after the date/time of first IV dose for IV dosing only patients and patients who transitioned to oral dosing and were in IV period,
- On or after the date/time of first oral dose for patients who transitioned to oral dosing and were in oral period.

An overview of AEs will be provided including counts and percentages of patients with the following:

- Any TEAEs (overall and by maximum severity)
- Any study drug-related TEAEs
- Any serious TEAEs (TESAEs)
- Any TEAEs leading to discontinuation of study drug
- Any TEAEs leading to discontinuation of study.

Counts and percentages of patients will also be presented by system organ class and preferred term for each of the categories in the overview. TEAEs and TESAEs will be also provided in patient-level listings.

If an adverse event has incomplete start or stop dates, dates will be imputed to determine whether the adverse event was treatment-emergent. Details on the imputation for incomplete dates will be provided in the final SAP to correspond to CRF design and instructions. Summaries will be performed by treatment/dose group.

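### Adverse events are shown by IV and oral period as percentages of patients over unequal follow-up with no person-time rate, and any oral-period change has no baseline at the start of oral dosing

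*SAP*

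**What the plan says.** **Entry and periods.** SAP 2.2.3 says: "All patients entering the study will continue receiving intravenous (IV) levosimendan weekly, and some of them will be transitioned to an oral dose of levosimendan". SAP 3.2.1 then sets the reporting columns: "Patients will be analyzed according to dose received, summarized by IV dosing period, oral dosing period, and in total".

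**Adverse events.** SAP 3.5.1 says: "An overview of AEs will be provided including counts and percentages of patients with the following", and lists any, related and serious TEAEs and those leading to discontinuation. The same measure is repeated by system organ class and preferred term. Tables 14.3.1 to 14.3.2.6 are the resulting outputs. No rate per unit of time appears in the SAP text or its table list.

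**Period lengths.** Under Protocol 1.1, patients who stay on IV are treated until two years after entry. Under Protocol 4.3, patients who transition continue for three years from the transition.

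**Baseline and clock.** SAP 3.1.3: "Baseline is defined as the last non-missing measurement prior to the first dose of study drug". SAP 3.1.1: "Analysis day will be calculated from the date of first dose of study drug (first IV dose or first oral dose, whichever occurs first").

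**Where baseline is used.** SAP 3.5.2 calculates change from baseline for each laboratory parameter at each scheduled visit. SAP 3.5 and Protocol 10.8 say that safety measures will be summarised by group. Protocol 10.9 promises descriptive efficacy statistics that include transition Week 0 and Week 6 or 8. The secondary objective in SAP 2.1.2 is whether effectiveness on daily oral levosimendan is sustained.

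**The concern.** The IV and oral columns will stand side by side in the primary-endpoint tables and will be read against each other. The percentage of patients with at least one event rises with time observed, so two columns covering different lengths of time can differ when the drug behaves identically in both. The reverse can also happen: a real difference can be hidden by a shorter period.

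The second part concerns the reference point. For a transitioned patient, the only defined baseline and Day 1 are set at the first dose by either route, which is an IV dose. A change computed at an oral-period visit therefore mixes whatever happened on IV with whatever happened on oral. A question about sustained effect on oral dosing needs a value taken at the start of oral dosing. The protocol schedules one at transition Week 0 (6MWT, KCCQ, NYHA class, laboratory tests, ECG), but the SAP does not name it as an analysis reference.

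**Working it through.** The plan gives no event count, event rate or sample size, so there is no figure of its own to reproduce. The check has three steps.

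**1. Effect of period length at a constant rate**

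Formula: percentage with at least one event = 1 − exp(−h × t), with the same hazard h in both periods and complete follow-up for t years. The hazards are assumptions. The maximum durations are from Protocol 1.1 (IV, 2 years) and 4.3 (oral, 3 years). The shorter durations are assumptions.

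At h = 0.6 per patient-year:
- IV 2 y: 1 − exp(−1.2) = 0.699, or 70%. Oral 3 y: 1 − exp(−1.8) = 0.8347, or 83%. Ratio 1.19.
- IV 0.5 y: 1 − exp(−0.3) = 0.259, or 26%. Oral 1.5 y: 1 − exp(−0.9) = 0.593, or 59%. Ratio 2.29.
- IV 2 y, oral 0.5 y: 70% against 26%. Ratio 0.37.

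Oral/IV ratio of crude percentages at other assumed hazards:

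| IV, oral (years) | h = 0.2 | h = 0.5 | h = 1.0 |
|---|---|---|---|
| 2, 3 | 1.37 | 1.23 | 1.10 |
| 1, 3 | 2.49 | 1.97 | 1.50 |
| 0.5, 3 | 4.74 | 3.51 | 2.41 |
| 2, 1.66 | 0.86 | 0.89 | 0.94 |
| 2, 0.5 | 0.29 | 0.35 | 0.46 |

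The true rate ratio is 1.00 in every cell, and events per patient-year would estimate it as 1.00 on average. The crude ratio runs from 0.29 to 4.74.

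**2. Why the direction cannot be fixed**

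SAP 3.3.5 imputes the last oral dose as 1 February 2023 for its residual group of patients. Counting to that date from the version dates in the protocol gives 737 days (25 January 2021), 729 days (2 February 2021) and 607 days (4 June 2021), or 2.02, 2.00 and 1.66 years. If oral dosing began no earlier than those dates, the residual group has at most about 1.7 to 2.0 years of oral exposure, not 3. A patient with nearly two years on IV could then have the shorter oral period, as in the 2 against 1.66 row. The documents do not give actual durations by period.

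**3. Where the single baseline reaches**

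| Item | Reference for the oral period | Affected? |
|---|---|---|
| TEAEs (SAP 3.5.1) | First oral dose | No |
| Concomitant medications (SAP 3.3.4) | First oral dose | No |
| Laboratory change (SAP 3.5.2) | Study baseline only | Yes |
| Summaries under SAP 3.5, Protocol 10.8 or 10.9 | None other defined | Yes, if change is shown |
| 6MWT, KCCQ, NYHA listings (SAP 3.4.2) | None needed for raw values | No |

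KCCQ has a further gap. Protocol 8.1.3.1 says: "The 6-point Likert scale will be replaced with the KCCQ instrument", and the amendment history places that change in Version 4.1. Patients enrolled before it have no KCCQ in this study from before their first dose, so Week 0 is their natural reference for any KCCQ change.

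**The case against.** The strongest reply is that the study is descriptive. SAP 3.1.5 rules out hypothesis tests, so no error rate is at stake. Oral exposure has its own table (14.1.4.2), so a careful reader can see that the periods differ in length. That stands, and it limits the matter to interpretation. It does not remove it, because mean exposure in one table does not let a reader convert percentages in another into rates.

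Several stronger readings are tempting and are not supported:

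- A reader might infer that the oral period has no clock or exposure of its own. Oral TEAEs and oral concomitant medications start at the first oral dose, and exposure days are summarised by route. What is missing is an oral analysis day and a rate that uses the exposure.
- A reader might infer that by-period tables in general compare oral values with a value from before IV. Change from baseline is specified for laboratory parameters only, and the listed laboratory outputs are listings of clinically significant values. Efficacy, vital signs and ECGs also go to listings. The baseline point matters for laboratory changes and for any summaries that are produced.
- A reader might infer that patients who already tolerated the drug dilute first-exposure events, or that the baseline is drug-free. Protocol 1.3.5 says all parent-study patients received an open-label lead-in infusion, so nobody rolling over from that study is newly exposed.
- A reader might want columns by parent-study arm. SAP 3.4.3 says: "No subgroup analyses will be performed for this study". The arm split of those who rolled over is not given, and nothing here requires reversing that choice.

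There are also fair objections to the remedy. Oral person-time rests partly on imputed dates and ignores interruptions (SAP 3.3.5). Week 0 falls 7 to 9 days after the last infusion, that is 168 to 216 hours. Against the 70 to 80 hour OR-1896 half-life in Protocol 1.3.1, this is 168/80 = 2.1 to 216/70 = 3.1 half-lives after the infusion ended. Week 0 may therefore sit at a low point of drug effect and flatter later oral values. Both objections stand and are met in the fix.

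**Conclusion.** The concern holds in a limited form. The certain part is the adverse event tables: they will be produced by period, they show percentages only, and the periods are unequal by design. At the protocol maxima and an assumed hazard of 0.6 per patient-year the distortion is modest (70% against 83%). With 0.5 and 1.5 years it is large (26% against 59%). These figures assume a constant, equal hazard and complete follow-up. Since actual durations are not given, neither the size nor the direction in this trial can be stated, and it would be wrong to conclude that oral dosing will look worse.

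The baseline part is conditional. It affects laboratory changes and any by-period change shown under SAP 3.5 or Protocol 10.8 and 10.9. SAP section 4 cites protocol v5.0, whereas the protocol in hand is v4.1, so the Week 0 commitment is read from v4.1.

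This is a worthwhile, cheap improvement to primary-endpoint tables, not a flaw that invalidates the study.

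**What to change.** **Rates.** Keep the percentages. For TEAEs, related TEAEs and SAEs, add by period:
- events per patient-year, using the exposure days already derived by route;
- first events per patient-year, with each patient's time cut at the first event in that period;
- exact 95% confidence intervals for both, noting that for all events the interval treats repeat events in one patient as independent.

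**Denominator rules.** State the by-period denominators. Flag every patient whose last oral dose date is imputed under SAP 3.3.5. State which period covers patients who re-start IV (Protocol 7.4), for events and for person-time. Under the current wording, anything after the first oral dose could be counted as oral. If the exposure formula is applied by route, first-to-last IV dates would also span the time on oral.

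**Oral reference.** Define an oral baseline as the last non-missing value before the first oral dose, normally transition Week 0, and an oral study day counted from that dose. Use them for any oral-period change, including KCCQ. Show the last office value taken on IV beside Week 0, so that a post-infusion low is not mistaken for benefit on oral.

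**Cost.** SAP wording, two derived variables and extra columns on planned tables, with no new data collection. The intervals will be wide, and part of the person-time will rest on imputed dates. Both should be visible to the reader.

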3.1.4 Summary Statistics

Categorical data will generally be summarized with counts and percentages of patients. The denominator used for the percentage calculation will be clearly defined. Continuous data will generally be summarized with descriptive statistics including n (number of non-missing values), mean, median, standard deviation, minimum, and maximum.

3.1.5 Hypothesis Testing

No hypothesis testing will be conducted for this study.

3.1.6 Evaluation of Site Effect

No evaluation of site-specific data for this study.

3.2 Analysis Populations

3.2.1 Safety Analysis Set (SAF)

The Safety Analysis Set (SAF) will consist of all patients who receive at least 1 dose of study drug. Patients will be analyzed according to dose received, summarized by IV dosing period, oral dosing period, and in total. The SAF will be used for the analysis of safety data.

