1. BACKGROUND INFORMATION

1.1 Transition from Weekly IV Levosimendan to Daily Oral Levosimendan Regimen

Tenax has recently licensed oral levosimendan from the Orion Corporation. The availability of an oral levosimendan capsule provides a convenient alternative to the weekly 24hr IV levosimendan in this study. Importantly, the safety concerns of local and systemic infections associated with IV administration through a PICC line or port-a-cath administration can be avoided. This protocol amendment identifies the procedures that will be used in transitioning consenting patients to a daily oral levosimendan dose regimen.

Patients that do not consent to this amendment will continue in the study on IV levosimendan. These patients will continue treatment until two years from the date of entry into the TNX-LVO-05 study (i.e., the final visit in the parent study, TNX-LVO-04), at which time they will be discontinued.

Numerous completed studies of oral levosimendan using immediate-release capsules provide a rich database of PK data (levosimendan and metabolites OR-1855 and OR-1896) in healthy volunteers and heart failure patients. These studies are listed in the updated Investigator's Brochure. Notably, Orion performed the PERSIST study in ~300 CHF patients receiving oral levosimendan at 1mg QD, 1mg BID, or placebo for 6 months.

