7.1 Treatment Transition: Weekly Intravenous to Daily Oral Levosimendan

All ongoing patients will be transitioned from IV to oral levosimendan over 6 weeks.

Any visit that occurs during the transition period that falls on the same day as a regularly scheduled visit (i.e. Week 3, 6, 12, 24, 48 or yearly) should include all the required procedures for both visits.

The first patient visit will occur 7-9 days following the completion of their last levosimendan infusion. Prior to starting any procedures related to the transitions, patients must sign an updated informed consent form.

Due to the ongoing pandemic (as of the date of this protocol) visits according to the [Time and Events Schedule](#) may be modified to accommodate patient scheduling. For example, a visit at transition Week 6 may be extended two additional weeks to accommodate either patient travel or hospital restrictions limiting patient visits.

Following successful transition to oral levosimendan, the port-a-cath should be removed for purposes of this study. During the transition (Weeks 0 to 6 or 8), the port-a-cath should be

maintained by the patient (i.e., flushing) according to the investigational site's institutional practices.

7.1.1 IV-Oral Transition Week 0

During this visit, the following procedures will be performed:

- Vital signs and ECG
- Physical Exam (including body weight)
- 6MWT
- Hematology and chemistry blood samples
- Pharmacokinetic sample
 - The sample should be taken before the patient consumes their first dose of oral levosimendan
- NYHA Functional Class
- Assess adverse events.
- Concomitant medications and/or procedures
- Kansas City Cardiomyopathy Questionnaire (KCCQ)
- Oral levosimendan

7.1.2 IV-Oral Transition Week 2

During this visit, the following procedures will be performed (this visit may be performed virtually, at the investigator's discretion):

- Vital signs
- Assess adverse events

7.1.3 IV-Oral Transition Week 4

During this visit, the following procedures will be performed (this visit may be performed virtually, at the investigator's discretion):

- Vital signs
- Assess adverse events
- Pharmacokinetic sample
 - *Note: if this visit is performed remotely and a home health nurse is unavailable to draw the PK sample, this sample may be missed*

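### The SAP's IV and oral safety columns hold different patients followed for different lengths of time, so their percentages support no IV-versus-oral safety reading in either direction

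*SAP*

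**What the plan says.** Everyone starts on IV and only part of the cohort moves. SAP 2.2.3: "All patients entering the study will continue receiving intravenous (IV) levosimendan weekly, and some of them will be transitioned to an oral dose". Protocol 7.1 states "All ongoing patients will be transitioned from IV to oral levosimendan over 6 weeks", and Protocol 1.1 adds "Patients that do not consent to this amendment will continue in the study on IV levosimendan". Read together, switchers are the patients who were still ongoing at Version 4.1 and consented. Those who decline may stay on IV for up to two years from study entry. Oral treatment may run for three years after transition (Protocol synopsis and 4.3).

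SAP 3.2.1 fixes the columns: "Patients will be analyzed according to dose received, summarized by IV dosing period, oral dosing period, and in total". SAP 3.5.1 fills them. The IV period counts events on or after "first IV dose for IV dosing only patients and patients who transitioned to oral dosing and were in IV period". The oral period counts events "On or after the date/time of first oral dose for patients who transitioned to oral dosing and were in oral period".

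The measure is a crude share: "An overview of AEs will be provided including counts and percentages of patients with the following". SAP 3.3.5 computes days of exposure and the table list has one exposure table per route, but no event rate is built from them. SAP 3.4.3 plans no subgroup analysis, SAP 3.1.5 no hypothesis test, and the Protocol synopsis no formal comparison.

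**The concern.** SAP 3.5.1 names two kinds of IV patient and then gives them one column. The neighbouring oral column contains only one of those kinds, observed later and for a different length of time. A difference between the columns can come from route, from who was left to switch, or from how long each period lasted, and the planned tables do not separate these.

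The baseline table would not reveal the selection. Baseline is the last value before first study drug (SAP 3.1.3), not at the switch, and SAP 3.3.3 lists only age, sex, race, weight, height and BMI.

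The primary objective is safety in extended use. The Protocol synopsis and 1.1 present oral dosing as avoiding line-related infection. Readers will set columns labelled by route against each other whether or not a test is planned.

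**Working it through.** **1. Who can be in each column.**

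| | IV column | Oral column |
|---|---|---|
| Left the study before the switch | yes | no |
| Declined to switch | yes | no |
| Switched | pre-switch time | from first oral dose |
| Re-started IV after a failed transition (Protocol 7.4) | column for later events not stated | column for later events not stated |

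A switcher cannot have died or left the study before the switch. A separate column for switchers' pre-switch time is therefore zero by construction for fatal events and for Table 14.3.2.6.

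Re-starters are a gap. SAP 3.2.1 analyses by dose received, which points to IV. For concomitant medications, SAP 3.3.4 ends the IV period at the first oral dose and treats everything afterwards as oral, which points to oral.

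**2. Does the layout push in one direction?** The plan has no figure to reproduce, so take a model with no route effect.

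Inputs:
- Death d = ln 2 / 5 = 0.139 per year, from the five-year survival below 50% in Protocol 1.2, taken at 50% with a constant hazard. It serves only as a model input.
- Assumptions: withdrawal w = 0.10 and serious events s = 0.5 per year. 10% decline to switch, unrelated to risk, with 0.5 year more on IV.
- A gamma risk multiplier (mean 1, variance θ = 0, 0.5, 1 or 2) acts on d, w and s.
- Pre-switch IV time a = 0.5, 1.0 or 1.8 years, or uniform on 0.25 to 2. Oral time b = 1.0, 1.7 or 3.0 years. The 1.7 is roughly from the Version 4.1 date of 04 June 2021 to the SAP's imputed last dose of Feb 1, 2023.

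Exit hazard x = d + w = 0.239; s + x = 0.739; s/(s + x) = 0.677.

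Mean risk of switchers = 1/(1 + θxa). For θ = 1, a = 1.0: 1/1.239 = 0.807, against 1.00 for all patients.

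*Share with a serious event, θ = 1, a = 1.0, b = 1.7.*
- IV, not declining: 0.677 × (1 − 1/1.739) = 0.288.
- IV, declining (1.5 years): 0.677 × (1 − 1/2.109) = 0.356.
- IV column: 0.9 × 0.288 + 0.1 × 0.356 = **29%**.
- Oral column: 0.677 × (1 − 1.239/(1.239 + 0.739 × 1.7)) = 0.677 × 0.503 = **34%**.

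*The same with a = 1.8, b = 1.0.*
- IV column: 0.9 × 0.386 + 0.1 × 0.426 = **39%**. Holding decliners to the Protocol's two-year limit still gives 39%.
- Oral column: 0.677 × (1 − 1.430/2.169) = **23%**.

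Deaths behave alike: about 12% IV against 14% oral in the first case, 18% against 8% in the second.

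With no variation in risk (θ = 0) the serious-event shares still move both ways: 36% against 48%, then 50% against 35%. That is exposure time alone.

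Across the 28 combinations (seven pairs of durations by four variances), oral looked better in 12 and worse in 16, for serious events and for deaths.

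**3. What person-time rates show.** Events per 100 person-years, θ = 1, a = 1.0, b = 1.7:
- Pooled IV: (0.9 × 0.404 + 0.1 × 0.552)/(0.9 × 0.897 + 0.1 × 1.282) = 0.418/0.935 = 44.7. Here events are (s/x)(1 − 1/(1 + xa)) and time is ln(1 + xa)/x.
- Switchers' own IV period: 0.5 × 0.807 = 40.4.
- Oral: 0.517/1.470 = 35.1.

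The gap with no route effect is 44.7 − 35.1 = 9.6. Splitting the IV column removes 44.7 − 40.4 = 4.3. The other 5.3 comes from further loss of high-risk patients during oral follow-up. A simulation with 400,000 patients per combination agrees within rounding (gap 9.5, about 4 removed).

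In all 21 combinations with varying risk, the oral rate was 0.59 to 0.90 of the pooled IV rate. With no variation the rates were equal.

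**The case against.** The strongest reply is that this is a small descriptive rollover study. The objective is safety of levosimendan in extended use, not IV against oral. Nothing is tested, a total column is kept, and the documents never call the IV column a comparator. Disposition shows who transitioned and why others left, exposure is tabulated by route, and TEAEs are listed by patient. At most 37 patients were randomized in the parent study (Protocol 1.3.5), so a careful reader could rebuild the groups from the listings. This stands as a limit on seriousness. It does not justify leaving the split to the reader when SAP 3.5.1 already names both groups.

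A reader might infer that oral is bound to look safer. The documents do not support that. The SAP reports crude percentages, these grow with follow-up, and oral follow-up can be the longer. Only person-time rates lean steadily towards oral, and only if risk varies between patients.

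A reader might also infer that the IV column is a sicker comparator. That is plausible for patients lost through death or illness, but nothing says decliners are sicker. Nor can expected mortality from the Protocol's background survival be taken as the size of a bias. It describes the disease generally, not responders who completed the parent study, and under one constant hazard for everyone survivors are no healthier than those who died.

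Finally, one might say that every death or study exit on IV belongs to someone absent from the oral column. That holds before the switch only, because re-starters can have such events on IV after oral exposure.

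**Conclusion.** The concern holds as a point about presentation. The IV and oral columns confound route with selection and with length of exposure, and the planned percentages cannot show which is at work. With no route effect, the modelled difference in serious events between the columns ran from 5 points against oral to 16 points in its favour in the two worked cases. Those sizes depend on assumed event, withdrawal and refusal rates and durations, which the documents do not give. The finding that the direction is not fixed does not depend on one choice: it appeared at every level of risk variation tried, including none. The composition of the columns needs no model; it follows from SAP 3.2.1 and 3.5.1 with Protocol 1.1 and 7.1. A bias in favour of oral is not demonstrated. The change is worth making because it is cheap and prevents an unsupported reading in either direction.

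**What to change.** In SAP 3.2.1, and in Tables 14.1.3, 14.1.4.1 and 14.3.1 to 14.3.2.6:

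- Show IV-only patients and switchers' IV period as separate columns. Keep oral and total.
- Add events per person-year from the exposure days in SAP 3.3.5. That formula ignores interruptions and imputes some last oral dose dates, so footnote both. Applied by route, first-to-last IV dose would also span a re-starter's oral time; exclude that interval.
- Read non-fatal adverse events within switchers, IV period against oral period.
- State which column holds events after a patient re-starts IV (Protocol 7.4), and align the period definitions in SAP 3.2.1, 3.3.4 and 3.5.1.
- State that death and study discontinuation before the switch cannot be compared between periods, because switching requires remaining on study.

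The cost is one more column, a rate line and a few sentences of SAP text, with no new data. The downside is smaller cells in a cohort of at most 37. The split does not remove selection from losses during oral follow-up, and the SAP should say so.
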